### **3.2 Sample Size**

Within each cohort subjects will be randomized to AMG 592 or placebo in a 5:2 ratio for cohorts 1, 2 and 3 and in a 3:1 ratio for cohorts 4 and 5. It is planned that approximately 29 subjects will be enrolled with 7 subjects assigned to each cohort (5 to AMG 592 and 2 to placebo) for cohorts 1, 2 and 3 and 4 subjects assigned to cohorts 4 and 5 (3 to AMG 592 and 1 to placebo). The total sample size may exceed 29 subjects and the number of subjects within a cohort may exceed the planned cohort size if, following a DLRM recommendation, additional dosing cohorts are added and/or existing cohorts are expanded, or if subjects are replaced as per protocol [Section 5.2.1](#). If additional subjects are added to a cohort the randomization ratio may not be preserved.

The sample size is based on practical considerations. With 5 subjects receiving AMG 592 per cohorts 1, 2, and 3, there is a 76% chance of at least 1 subject experiencing an adverse event, if the true event rate is 25%. The chance of at least 1 subject experiencing an adverse event will be 67% if the event rate becomes 20%. With a total of 21 subjects planned to receive AMG 592 in the study, there is a 19% chance of at least 1 subject experiencing an adverse event with a true event rate of 1%. The chance of at least 1 subject experiencing an adverse event will be 66% if the true event rate becomes 5%.

## **4. Covariates and Subgroups**

### **4.1 Planned Covariates**

There are no pre-specified covariates.

### **4.2 Subgroups**

There are no pre-specified subgroup analyses.

## **5. Definitions**

### **5.1 Basic Definitions**

#### **Investigational Product (IP)**

The term 'investigational product' is used in reference to AMG 592 all dose levels and placebo.

#### **Prior Medication and Concomitant Medications**

Prior medication is defined as any medication with start date prior to the first dose date of investigational product and ended before the 1st IP dose. Concomitant medication is defined as any medication with start date prior to the first dose date of investigational product but which continued to be taken after the first dose of investigational product or

---

any medication with start date on or after first dose date of investigational product and up to and including 42 days after the last dose date of investigational product.

## **5.2 Study Points of Reference**

### **Baseline**

For any variable, baseline is the last assessment taken prior to or on the first investigational product administration unless stated otherwise; for subjects who did not receive any investigational product, baseline is the last assessment on or before enrollment date.

### **Baseline for Pharmacodynamics (PD)**

For lymphocyte subsets, if 2 or more time points are collected at day -1 and day 1 pre-dose, then the average of those time points will be reported.

### **Baseline medication**

Baseline medication is defined as any medication with start date on or before Study Day 1 and ongoing while on study. If the medication is taken on the same day as the first dose and the exact time relative to the first dose is unknown, it will be assumed to have been taken prior to the first dose of IP.

### **Study Day**

Study day is defined as the number of days from Study Day 1.

Post study day 1: study day = (date of interest – date of Study Day 1) + 1

Pre study day 1: study day = (date of interest – date of Study Day 1)

### **Study Day 1**

Study day 1 is defined as the first day of administration of the investigational product or the day of enrollment if the subject does not receive any investigational product. The day prior to Study Day 1 is considered as Day -1.

### **End of Study Date**

The end of study date is recorded on the End of Study CRF.

### **Enrollment (Randomization) Date**

The date on which a subject is assigned to receive AMG592 or placebo through the IRT.

### **End of Investigational Product Date**

The date on which a subject is administered the last dose of investigational product.

### **Duration of Treatment-emergent Injection Site Reaction (ISR)**

---

Duration = (min (ISR end date, EOS date) – ISR start date) + 1.

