3.3 Risk Assessment

Repeated SC doses of up to [REDACTED] µg administered [REDACTED] and [REDACTED] have been studied for up to **12 weeks** in subjects with rheumatoid arthritis and SLE. **In addition, repeated SC doses of up to [REDACTED] µg [REDACTED] for up to 52 weeks have been studied in subjects with cGVHD.** The most **frequent** adverse event was mild (grade 1 or 2) painless erythema at or near the injection site, sometimes accompanied by pruritus, that was self-resolving. Two serious hypersensitivity reactions to AMG 592 have been reported, though none occurred in the current study. No clinically significant therapeutic related abnormalities in electrocardiograms (ECGs), hematological or biochemical laboratory investigations, or vital signs have been reported. No adverse events greater than grade 2 assessed as related to AMG 592 nor any deaths have occurred in the phase 1b part of the current study in SLE patients. More detailed information about the known and expected risks

and reasonably expected adverse events associated with AMG 592 may be found in the Investigator's Brochure.

4. Objectives, Endpoints and Hypotheses

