### **8.3 Handling of Missing and Incomplete Data**

All endpoints in the study will be analyzed as-is and no imputation is planned.

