## **9. Statistical Methods of Analysis**

### **9.1 General Considerations**

Descriptive statistics will be provided for selected demographics, safety, PK, PD, immunogenicity, efficacy, and biomarker data. Descriptive statistics on continuous measurements will include means, medians, Q1, Q3, standard deviations, standard errors and ranges, while categorical data will be summarized using frequency counts and percentages. Data will be presented and summarized by treatment and also by time as appropriate.

For the DLRM analyses safety data will be listed and figures may be provided. The scope of review includes all available study data including demographics, medical history, concomitant therapies, adverse events, electrocardiograms, vital signs, laboratory results, and emerging pharmacokinetic and pharmacodynamics data.

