### **9.6.2 Adverse Events**

The Medical Dictionary for Regulatory Activities (MedDRA) version 24.0 or later will be used to code all events categorized as adverse events, all disease-related events to a system organ class and a preferred term. The severity of each adverse event will be graded using CTCAE criteria version 4.03.

Subject incidence of all treatment-emergent, serious treatment-emergent, treatment-related, serious treatment-related, disease-related treatment-emergent, those leading to withdrawal from investigational product, and fatal adverse events will be tabulated by system organ class in alphabetical order, preferred term and grade in descending order of frequency. Subject incidence of treatment-emergent adverse events identified by

COVID-19 standardized MedDRA queries and serious adverse events occurring on or after the COVID-19 infection will also be summarized.

Subject incidence of treatment-emergent events of interest (standardized MedDRA queries and/or Amgen Medical Queries) will also be summarized according to their categories, preferred term, and worst severity grade. Events of interest could include but are not limited to Hypersensitivity, Tachyarrhythmias, Tachypnea, Hematopoietic Cytopenia, Drug Reaction with Eosinophilia, Leucocyte Changes, Infection and Infestation, Cytokine Release Syndrome, and Injection Site Reaction. Number of episodes and duration of treatment-emergent injection site reactions will be further summarized by treatment group.

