## 12. Appendices

### **Appendix A. Concomitant Medications/Adverse Event Missing Value Imputation Imputation Rules for Partial or Missing Stop Dates**

If the month and year are present, impute the last day of the month. If only the year is present, impute December 31 of that year. If the stop date is entirely missing, assume the event or medication is ongoing. If a partial or complete stop date is present and the 'ongoing' or 'continuing' box is checked, then it will be assumed that the AE or conmed stopped and the stop date will be imputed, if partial.

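### Injection-site reaction duration counts month-end and end-of-study dates as observed resolutions, which distorts the mean, SD and maximum, and SAP 8.3 contradicts the date rules

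*SAP*

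**What the plan says.** SAP 5.2 gives the formula: "Duration = (min (ISR end date, EOS date") minus the ISR start date, plus one. It has no rule for partial, missing or ongoing stop dates.

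SAP Appendix A, whose title covers adverse events as well as concomitant medications, completes stop dates in three ways:
- Day missing: "If the month and year are present, impute the last day of the month".
- Month and day missing: "If only the year is present, impute December 31 of that year".
- Whole date missing: "If the stop date is entirely missing, assume the event or medication is ongoing".

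Appendix A also completes partial start dates, mostly to the date of first dose or the first of the month.

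SAP 8.3 states: "All endpoints in the study will be analyzed as-is and no imputation is planned".

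SAP 9.6.2 puts the duration to use: "Number of episodes and duration of treatment-emergent injection site reactions will be further summarized by treatment group". Under SAP 9.1, "Descriptive statistics on continuous measurements will include means, medians, Q1, Q3, standard deviations, standard errors and ranges". Protocol 3.3 describes the most frequent event so far: "adverse event was mild (grade 1 or 2) painless erythema at or near the injection site, sometimes accompanied by pruritus, that was self-resolving".

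**The concern.** Rules that push a stop date late are reasonable for deciding whether an event or medication falls inside a reporting period. They are not reasonable for measuring how long a reaction lasted. Once a completed date enters the 5.2 formula, the result reflects the calendar or the subject's follow-up time, not the reaction.

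Three different situations end up looking like observed resolutions: a resolved reaction whose end day was not recorded, a reaction whose end date is blank, and a reaction still present at end of study. The first two lengthen the duration. The third shortens it, because the reaction is treated as ending on the day observation stopped. No section flags, censors or counts any of them.

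At stake is the description of tolerability by treatment group for the event the protocol names as most frequent and calls self-resolving. Planned active groups are 5 subjects (cohorts 1 to 3) or 3 subjects (cohorts 4 and 5). One blank field could produce a maximum of several months that seems to contradict the protocol's description.

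**Working it through.** The plan states no figure for ISR duration, so there is none to reproduce. The check puts completed dates into the plan's formula.

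**Inputs from the documents.** End of study is at week 18, Day 127 (Protocol Table 2-2). Dosing runs from Day 1 to Day 85 (Protocol Table 2-1), so weekly dosing gives (85 − 1)/7 + 1 = 13 doses and fortnightly dosing (85 − 1)/14 + 1 = 7. Active group sizes are 5 or 3 (SAP 3.2).

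**Assumptions.** The true duration d is 4 days (range 2 to 14 below). There is one reaction per dose in every subject, and one incomplete stop date in the group. The documents give none of these, and the cohorts' schedules are blacked out.

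**Step 1: completed duration x.** A missing stop date gives 127 − onset day + 1: 127 days for onset on Day 1, 120 for Day 8 and 43 for Day 85. A month-only date adds the days from the true stop to month-end. Averaged over a 365-day year this is (7 × 465 + 4 × 435 + 378)/365 = 14.7 days, so x averages 18.7 when d = 4. Onset on the 3rd of a 31-day month gives x = 29, well above that average.

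**Step 2: group mean.** With k episodes, mean = ((k − 1)d + x)/k = d + (x − d)/k.

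| Episodes k | Missing stop, Day 1 onset (x = 127) | Month-only, average (x = 18.7) | Month-only, onset on 3rd (x = 29) |
|---|---|---|---|
| 65 (5 subjects, weekly) | (64×4 + 127)/65 = 5.9 | 4 + 14.7/65 = 4.2 | 4 + 25/65 = 4.4 |
| 39 (3 subjects, weekly) | (38×4 + 127)/39 = 7.2 | 4 + 14.7/39 = 4.4 | 4 + 25/39 = 4.6 |
| 35 (5 subjects, fortnightly) | 4 + 123/35 = 7.5 | 4 + 14.7/35 = 4.4 | 4 + 25/35 = 4.7 |
| 21 (3 subjects, fortnightly) | 4 + 123/21 = 9.9 | 4 + 14.7/21 = 4.7 | 4 + 25/21 = 5.2 |
| 5 (few reactions) | 4 + 123/5 = 28.6 | 4 + 14.7/5 = 6.9 | 4 + 25/5 = 9.0 |

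**Step 3: sensitivity, missing stop date.**
- d = 2: 2 + 125/65 = 3.9 days and 2 + 125/39 = 5.2 days.
- d = 14: 14 + 113/65 = 15.7 days and 14 + 113/39 = 16.9 days.
- Day 85 onset, d = 4: 4 + 39/65 = 4.6 days and 4 + 39/39 = 5.0 days.

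**Step 4: other statistics.** If all other episodes last exactly d, one value x gives SD = (x − d)/√k: 123/√65 = 15.3 days and 123/√39 = 19.7 days, where the true SD is 0. The maximum becomes 127. The median stays at 4 for any k of 3 or more.

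**The case against.** The strongest reply is that SAP 5.2 never cites Appendix A and 8.3 rules out imputation, so a partial date might simply yield no duration. That stands in part: using Appendix A dates is the plain reading of an appendix that covers adverse events by title, not an explicit cross-reference. But the SAP does not limit Appendix A to classification, and the 5.2 formula sends any episode without an end date to the end-of-study date.

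The second reply is that incomplete dates should be rare. Protocol Appendix 4 requires onset and resolution dates, adverse events are collected at least weekly during treatment and followed to resolution or stabilisation, and SAP 7.2 resolves data issues before lock. This lowers the likelihood. It does not remove the rule, and cleaning cannot supply an end date for a reaction still present at end of study.

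The third reply is that the median and quartiles are planned, there is no formal hypothesis, and dose review after week 4 uses listings and plots. That stands, and it limits the consequence.

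A reader might go further in two ways that the documents do not support:
- **That one blank date typically multiplies the reported mean.** For one subject's 13 weekly episodes, (12×4 + 127)/13 = 13.5 days against 4. But SAP 9.6.2 summarises by treatment group, where the same assumptions give 5.9 or 7.2. Multiplication needs few episodes or very short reactions.
- **That more injections bias one group against another.** If each episode has probability p of an incomplete date, the expected bias in the mean is p(x − d), whatever the number of episodes. Extra incomplete dates are diluted in proportion. With schedules blacked out, no difference between dose groups can be shown.

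**Conclusion.** The point holds as a defect in a descriptive tolerability summary. The formula, read with Appendix A, turns unknown and unresolved end dates into observed resolutions, and 8.3 contradicts the appendix. Incomplete stop dates bias the mean, SD and maximum upward, and truncation at end of study understates reactions still ongoing.

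Under the base assumptions, one missing stop date from Day 1 raises the group mean by 1.9 days (65 episodes) or 3.2 days (39 episodes), and by more with fewer episodes. An average month-only date adds about 0.2 to 0.4 days at those counts. These sizes rest on assumed durations, episode counts and a single incomplete date. The direction of each error does not. No dosing decision or hypothesis test depends on the result.

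**What to change.** 1. **SAP 5.2:** state that Appendix A dates serve only to classify events and medications and do not enter ISR duration. Summarise duration for episodes with complete start and stop dates.
2. **SAP 9.6.2:** beside that summary, report by treatment group the number of episodes with partial or missing dates and the number ongoing at end of study. Show ongoing episodes as censored (at least x days), neither resolved nor dropped. This part is essential: a complete-dates summary alone would omit unresolved reactions, possibly the longest, and bias duration downward.
3. **SAP 8.3:** reword so that the no-imputation statement and the Appendix A date rules agree.

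A Kaplan-Meier median is optional. Repeated episodes within 3 to 5 subjects are correlated, so its precision should not be taken at face value.

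The cost is a few lines of SAP wording and a small programming change. The downside is that a few episodes give a censored time or a count instead of a value.

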### Duration of IP exposure

The duration of IP exposure will be derived as earliest date of the last IP administration plus <dosing frequency> - 1, end of study, whichever occurs first, minus the date of first IP administration plus 1 day, where dosing frequency is 7 for QW dosing and 14 for Q2W dosing.

### Study Visit

Since the actual visit for a subject may not exactly coincide with their scheduled visit date, the actual visit date is mapped to the analysis visit as per the analysis visit windows described in [Appendix B](#).

## 5.3 Arithmetic Calculations

### Change From Baseline

Change from baseline is the arithmetic difference between post-baseline and baseline.

### Fold Change From Baseline

Fold change from baseline equals the post-baseline value divided by the baseline value. If the change from baseline is not equal to 0 and the baseline value is 0, then fold change is not defined. If the change from baseline is equal to 0 and the baseline value is also 0, then fold change is 1.

### Number of Days on Investigation Product

Number of days on IP is defined as last dose date – first dose date +1.

### Treg to Tcon Ratio

The ratio is defined as number of Tregs divided by number of Tcons. When the value of Tcon is 0, then the ratio of Treg to Tcon is reported as 1.

## 5.4 Definitions of Study Endpoints

### Systemic Lupus Erythematosus Disease Activity Index 2000

The SLEDAI-2K is a global index that evaluates disease activity and includes 24 items collecting specific manifestations in 9 organ systems: neurological, musculoskeletal, renal, mucocutaneous, general, heart, respiratory, vascular, and hematological. The maximum score is 105.

### **Incidence of Events of Interest**

Incidents of events of interest such as selected adverse events or intolerable PD levels will be identified after safety data is collected and before each DLRM convenes.

### **Treatment-emergent Adverse Event (TEAE)**

A treatment-emergent adverse event is any adverse event starting or worsening on or after the first dose of investigational product (as determined by the flag indicating if the adverse event started prior to the first dose or not on the Adverse Events eCRF) and up to and including 42 days after the last dose date or the End of Study date on eCRF form, whichever is earlier.

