9.2.1.3 Medical History

The Investigator or designee will collect a relevant medical and surgical history that started within 5 years or as necessary for chronic or co-morbid conditions prior to enrollment through the start of the adverse event reporting period. Medical history will include information on the subject's concurrent medical conditions. Record all findings on the medical history CRF. In addition to the medical history above, SLE history must date back to the original diagnosis. The current toxicity grade will be collected for each condition that has not resolved.

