9.2.3.1 Adverse Events

9.2.3.1.1 Time Period and Frequency for Collecting and Reporting Safety Event Information

9.2.3.1.1.1 Disease-related Events

Disease-related events are defined in [Appendix 4](#).

The investigator is responsible for ensuring that all disease-related events observed by the investigator or reported by the subject that occur after the first dose of investigational product(s)/study treatment/protocol-required therapies through the safety follow-up visit are recorded using the Event CRF.

All serious disease-related events will be recorded and reported to the sponsor or designee within 24 hours. The investigator will submit any updated serious disease-related event data to the sponsor within 24 hours of it being available.

Disease-related events assessed by the investigator to be more severe than expected and/or related to the investigational product(s)/study treatment/protocol-required therapies, and determined to be serious, must be reported on the Event CRF as serious adverse events and recorded and reported per [Sections 9.2.3.1.1.3](#) and [Appendix 4](#).

Disease-related events pre-defined for this study include: lupus-related joint pain, joint stiffness, joint swelling, rash, alopecia, and mucosal ulcers.

9.2.3.1.1.2 Adverse Events

The adverse event grading scale to be used for this study will be the CTCAE and is described in [Appendix 4](#).

The investigator is responsible for ensuring that all adverse events observed by the investigator or reported by the subject that occur after first dose of investigational product through the safety follow-up visit are reported using the Event CRF.

9.2.3.1.1.3 Serious Adverse Events

The investigator is responsible for ensuring that all serious adverse events observed by the investigator or reported by the subject that occur after signing of the informed consent through safety follow-up visit are reported using the Event CRF.

All serious adverse events will be collected, recorded and reported to the sponsor or designee within 24 hours, as indicated in [Appendix 4](#). The investigator will submit any updated serious adverse event data to the sponsor within 24 hours of it being available.

The criteria for grade 4 in the CTCAE grading scale differs from the regulatory criteria for serious adverse events. It is left to the investigator's judgment to report these grade 4 abnormalities as serious adverse events.

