
Any abnormal laboratory test results (hematology, clinical chemistry, or urinalysis) or other safety assessments (eg, electrocardiogram [ECG], radiological scans, vital signs measurements), including those that worsen from baseline, that are considered clinically significant in the medical and scientific judgment of the investigator (ie, not related to progression of underlying disease).
 
Exacerbation of a chronic or intermittent pre-existing condition including either an increase in frequency and/or intensity of the condition.
 
New conditions detected or diagnosed after study treatment administration even though it may have been present before the start of the study.
 
Signs, symptoms, or the clinical sequelae of a suspected drug-drug interaction.
 
Signs, symptoms, or the clinical sequelae of a suspected overdose of either study treatment or a concomitant medication. Overdose per se will not be reported as an adverse event/serious adverse event unless it is an intentional overdose taken with possible suicidal/self-harming intent. Such overdoses are to be reported regardless of sequelae.
 
“Lack of efficacy” or “failure of expected pharmacological action” per se will not be reported as an adverse event or serious adverse event. Such instances will be captured in the efficacy assessments. However, the signs, symptoms, and/or clinical sequelae resulting from lack of efficacy will be reported as adverse event or serious adverse event if they fulfill the definition of an adverse event or serious adverse event.

Approved

Events NOT Meeting the Adverse Event Definition

Medical or surgical procedure (eg, endoscopy, appendectomy): the condition that leads to the procedure is the adverse event.

Situations in which an untoward medical occurrence did not occur (social and/or convenience admission to a hospital).

Anticipated day-to-day fluctuations of pre-existing disease(s) or condition(s) present or detected at the start of the study that do not worsen.

Definition of Serious Adverse Event

A Serious Adverse Event is defined as any untoward medical occurrence that meets at least 1 of the following serious criteria:

Results in death (fatal)

Immediately life-threatening

The term "life-threatening" in the definition of "serious" refers to an event in which the subject was at risk of death at the time of the event. It does not refer to an event, which hypothetically might have caused death, if it were more severe.

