The investigator will then record all relevant adverse event/disease-related event/serious adverse event information in the Event case report form (CRF).

- Additionally, the investigator is required to report a fatal disease-related event on the Event CRF.

The investigator must assign the following adverse event attributes:

- Adverse event diagnosis or syndrome(s), if known (if not known, signs or symptoms);
- Dates of onset and resolution (if resolved);
- Severity (or toxicity defined below);
- Assessment of relatedness to investigational product, other protocol-required therapies; and
- Action taken.

If the severity of an adverse event changes from the date of onset to the date of resolution, record as a single event with the worst severity on the Event CRF.

It is not acceptable for the investigator to send photocopies of the subject's medical records to sponsor in lieu of completion of the Event CRF page.

If specifically requested, the investigator may need to provide additional follow-up information, such as discharge summaries, medical records, or extracts from the medical records. In this case, all subject identifiers, with the exception of the subject number, will be blinded on the copies of the medical records before submission to Amgen.

The investigator will attempt to establish a diagnosis of the event based on signs, symptoms, and/or other clinical information. In such cases, the diagnosis (not the individual signs/symptoms) will be documented as the adverse event/serious adverse event.

Evaluating Adverse Events and Serious Adverse Events

Assessment of Severity

The investigator will make an assessment of severity for each adverse event and serious adverse event reported during the study. The assessment of severity will be based on:

The Common Terminology Criteria for Adverse Events (CTCAE), version 4.03 which is available at the following location:

http://ctep.cancer.gov/protocolDevelopment/electronic_applications/ctc.htm.

Approved

Assessment of Causality

The investigator is obligated to assess the relationship between investigational product, protocol-required therapies, and/or study-mandated procedure and each occurrence of each adverse event/serious adverse event.

Relatedness means that there are facts or reasons to support a relationship between investigational product and the event.

The investigator will use clinical judgment to determine the relationship.

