**2. Objectives, Endpoints and Hypotheses**

**2.1 Objectives and Endpoints/Estimands**

Objectives	Endpoints
Primary	

To evaluate the safety and tolerability of subcutaneous (SC) dose administrations of AMG 592 in subjects with systemic lupus erythematosus (SLE)

	

Treatment-emergent adverse events

Clinically significant changes in physical examinations, vital signs, and laboratory safety tests

Secondary	

To characterize the pharmacokinetic (PK) profile following treatment with AMG 592

	

AMG 592 serum concentration and PK parameters including, but not limited to, maximum observed concentration (Cmax), the time of maximum observed concentration (Tmax), and area under the concentration-time curve over a dosing interval (AUCtau) after the first and last doses

To evaluate anti-AMG 592 antibody formation

	

Incidence of anti-AMG 592 antibodies

Cross-reactivity of anti-AMG 592 antibodies with human interleukin-2 (IL-2)

Incidence of anti-AMG 592 and anti-IL 2 neutralizing antibodies

Exploratory	

To explore the effect of treatment with AMG 592 on measures of inflammation at various time points

	

Change from baseline in anti-double stranded DNA (anti-dsDNA), and C3 and C4 complements at all time points collected

To explore the effect of treatment with AMG 592 on measures of disease activity at various time points

	

SLEDAI-2K score and change from baseline at all time points collected

To evaluate the immunological effects of AMG 592

	

Fold changes from baseline of Treg, Tcon, and NK absolute cell counts (cells/<math>\mu</math>L) after AMG 592 administration

Changes in Treg/Tcon ratio after AMG 592 administration

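### SAP 5.4 treats worsening after first dose as treatment-emergent but tests only for start before first dose, so a serious adverse event that begins in screening and worsens on treatment is not counted

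*SAP*

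**What the plan says.** Treatment-emergent adverse events are a primary endpoint (Protocol 4.1; SAP 2.1). SAP 5.4 defines one as "any adverse event starting or worsening on or after the first dose of investigational product" and then says in parentheses how this is decided: "as determined by the flag indicating if the adverse event started prior to the first dose or not". The SAP gives no other worsening rule: no grade comparison, no date of worsening and no reference to a baseline grade. SAP 5.4 also defines a treatment-related event as a subset of treatment-emergent events.

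The protocol governs what reaches the Event CRF, and with what onset:

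- Protocol 9.2.3.1.1.2 collects adverse events "that occur after first dose of investigational product through the safety follow-up visit are reported using the Event CRF". Section 9.2.3.1.1.1 sets the same starting point for disease-related events.
- Protocol 9.2.3.1.1.3 collects serious adverse events from the signing of consent.
- Protocol 9.2.1.3 places earlier conditions in medical history: "The current toxicity grade will be collected for each condition that has not resolved".
- Protocol Appendix 4 lists among the events that are adverse events: "Exacerbation of a chronic or intermittent pre-existing condition including either an increase in frequency and/or intensity of the condition".
- Protocol Appendix 4 also says that, if severity changes between onset and resolution, the site should "record as a single event with the worst severity on the Event CRF". The attributes it lists include dates of onset and resolution but no date of worsening.

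**The concern.** The definition has two limbs, starting and worsening, and the test serves only the first. A programmer who follows the parenthesis literally will class any event with pre-dose onset as not treatment-emergent, whatever happened to it afterwards. The single-record rule in Appendix 4 compounds this: the record keeps its pre-dose onset while its grade is raised to the worst seen, so nothing on it shows when the grade rose.

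At stake is a primary endpoint in cohorts with 5 or 3 subjects on AMG 592. The error runs one way: a start-only rule can lose worsened events and cannot add any. A lost event would be missing from the treatment-emergent and serious treatment-emergent tables of SAP 9.6.2. It would also be missing from the treatment-related and serious treatment-related tables, even if the investigator judged the worsening to be caused by the product.

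**Working it through.** This is mainly a question of definitions, so the check traces each type of event through the collection rules and then through the flag.

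1. **Non-serious event that starts after first dose and later worsens.** The flag shows it did not start before dosing. It counts, at its worst grade. Nothing is lost.
2. **Condition present before dosing, held in medical history, that worsens after dosing.** It was not an adverse event record before dosing, because non-serious collection begins at first dose. The exacerbation meets the adverse event definition itself, so it is recorded as an event occurring after first dose. The flag counts it. It would be lost only if a site entered the underlying condition's pre-dose date as the onset.
3. **Disease-related event** (lupus joint symptoms, rash, alopecia, mucosal ulcers). It is collected only from first dose and tabulated separately. If worse than expected or thought related to product, it becomes an adverse event, and item 2 applies.
4. **Serious adverse event with onset between consent and first dose that worsens after dosing.** It is already on the Event CRF with a pre-dose onset. The severity rule keeps one record at worst grade. The flag says it started before dosing, so it is not treatment-emergent and therefore cannot be treatment-related. It is lost.

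Only item 4 is exposed by the rules as written. The window for it is at most the 28-day screening period (Protocol 9.1.1).

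**Size of one omission**, using the planned numbers on AMG 592 (Protocol 10.1):

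- Cohorts 1 to 3: 1/5 = 20 percentage points.
- Cohorts 4 and 5: 1/3 = 33 percentage points.
- All AMG 592: 1/21 = 4.8 percentage points.

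These apply to a preferred-term row when the subject has no other treatment-emergent event of that term. Because SAP 9.6.2 tabulates subjects, overall incidence changes only if the subject has no other treatment-emergent event at all. The fractions are the effect of any single omitted subject; they do not measure how often this rule omits one.

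**The plan's own figures.** Protocol 10.1 and SAP 3.2 give the chance of seeing at least one event, 1 − (1 − p)^n:

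| n | p | Stated | Recomputed |
|---|---|---|---|
| 5 | 25% | 76% | 76.3% |
| 5 | 20% | 67% | 67.2% |
| 21 | 1% | 19% | 19.0% |
| 21 | 5% | 66% | 65.9% |

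All four reproduce, and the point does not depend on them. As an illustration only, suppose the flag missed a share f of qualifying events, so that p becomes p(1 − f). At f = 5% the four values are 74.2%, 65.1%, 18.2% and 64.0%; at f = 20% they are 67.2%, 58.2%, 15.5% and 57.6%. The documents give no value for f. With only item 4 exposed, it should lie near or below the low end.

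**The case against.** The strongest reply is that the exposed class is almost empty. A serious event would have to start in screening, remain unresolved at dosing, leave the subject eligible at the screening and day -1 checks, and then worsen. Exclusion criteria 206, 211 and 231 bar serious infection within 8 weeks of day 1, significant concurrent conditions and any disorder judged to pose a risk. Such events must still reach the sponsor within 24 hours, and dose level review meetings look at all available adverse event data (Protocol Appendix 3; SAP 9.1). Escalation decisions therefore do not depend on the flag. The eCRF and its completion guide are not among the documents, so a worsening field or a new-record instruction may already exist. All of this stands, and it limits the point to a minor one. It does not repair the SAP, whose stated rule still contradicts its own definition.

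A reader might infer something stronger: that worsened events in general drop out of the primary endpoint, and that lupus patients, who enter with ongoing conditions, are widely affected. The documents do not support that. Medical-history conditions are not adverse event records, so the single-record rule does not merge a later exacerbation with them; the exacerbation is a new event with its own onset. The wider class arises only if sites enter the condition's pre-dose date. Neither document states which date to use, so that cannot be excluded, but it would be a data-entry practice and does not follow from the stated rule.

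**Conclusion.** The mismatch is real and minor. Applied literally, the rule cannot count a pre-dose event that worsens on treatment. The class shown to be exposed is serious adverse events with onset between consent and first dose. The number of subjects is unknown, probably very small and possibly zero. Any bias in treatment-emergent incidence is downward. The rule applies to both arms, so the documents do not show which way a contrast with placebo would move.

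This rests on two assumptions: that sites date an exacerbation of a medical-history condition from the worsening, and that no eCRF field or guide outside these documents already captures worsening. If the first fails, the exposed class is larger; if the second fails, the gap may already be closed in practice.

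**What to change.** - **SAP 5.4:** define a treatment-emergent adverse event as one flagged as not starting before first dose, or one that started before first dose and whose grade increases on or after it, keeping the present 42-day and end-of-study limits.
- **Protocol Appendix 4 and the CRF completion instructions:** enter such an increase as a new Event CRF record with onset at the date of worsening, leaving the pre-dose record and its grade intact. The SAP sentence alone is not enough, because the single-record rule overwrites the pre-dose grade needed for the comparison.
- **Medical-history conditions:** state that the onset of an exacerbation is the date of worsening. The pre-dose toxicity grade already collected allows a check.
- **Before final lock:** list the records flagged as starting before first dose and query sites on grade at first dose and any later increase. SAP 7.2 already requires outstanding data issues to be resolved by then.

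The cost is one SAP sentence, one recording instruction aligned with Appendix 4, and a few data queries. Reported incidence may rise slightly. No sample-size figure changes.
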